# 9.2.2 Serious adverse events (SAEs)

A serious adverse (device) event (SA(D)E) is a serious (leading to hospitalization or (near)-death) unfavorable and unintended sign (including an abnormal finding), symptom, or disease temporally associated with the clinical trial whether or not related to a failure of the device to alarm. A SAE will be reported within 7 days to the METC . All subjective or presumed complaints will be reported. We do not expect serious adverse events causally related to NightWatch (SADE). Previous trials (LICSENSE Phase I-III) have indicated that the NightWatch is tolerated well with respect to comfort and skin reactions.

# 9.2.3 Suspected unexpected serious adverse reactions (SUSARs)

Not applicable.

# 9.3 Annual safety report

Not applicable.

# 9.4 Follow-up of adverse events

All AEs will be followed until they have abated, or until a stable situation has been reached. Depending on the event, follow up may require additional tests or medical procedures as indicated, and/or referral to the general physician or a medical specialist.

9.5 [Data Safety Monitoring Board (DSMB) / Safety Committee] Not applicable.

#### **10 STATISTICAL ANALYSIS**

#### 10.1 Primary study parameter(s)

Performance of the algorithms (sensitivity, positive predictive value, false alarm rate and % time with valid signal allowing proper detection) will be expressed using descriptive statistics.

#### 10.2 Secondary study parameter(s)

Methods triangulation will be conducted for this study, which means that there will be two or more research methods applied in one study [30,31]. After analysis the results will be combined, leading to a deeper understanding concerning the feasibility parameters.

Feasibility and utility of the NightWatch will be presented, using descriptive statistics (see table 3). To calculate differences in pre- and post-measurements, a paired samples T-test will be applied (in case of normal distribution). Multiple imputation test will be applied in case of missing data. Differences in outcome will be tested through a post-hoc test.

#### Semi-structured interviews

Data from the semi-structured interviews will be analyzed using a thematic analysis approach [32]. Thematic analysis is a flexible method for identifying and analyzing patterns within data. All interviews will be audiotaped, and transcribed verbatim; NVivo software (QSR International Pty Ltd, 2012) will be used in the analysis process. Thematic analysis consist of six steps: getting familiar with the data, generating codes, searching for themes, reviewing themes, defining theme, and representing results [32].

#### **Group session**

A focus group session with subjects, parents/guardians and professionals will be organized. After consent of the participants, the session will be recorded on video and transcribed verbatim will be used for further thematic analysis.

Table 3. Analysis for feasibility parameters

Feasibility parameter	Source	Analysis
Acceptability		
Satisfaction	- Survey T2	- Descriptive statistics 
	- Interview	- Thematic analysis
Intent to continue use	- Survey T0	- Descriptive statistics 
	- Interview	- Thematic analysis
Expectations	- Survey T0	- Descriptive statistics 
Demand		
Actual use	- Diary	- Descriptive statistics 
	- Interview	- Thematic analysis
Perceived demand	- Survey T0	- Descriptive statistics 
	- Survey T2	- Descriptive statistics 
Implementation		
Degree of execution	- Diary	- Descriptive statistics 
	- Interview	- Thematic analysis
	- Survey T2	- Descriptive statistics 
Success or failure of execution	- Interview	- Thematic analysis
	- Survey T2	- Descriptive statistics 
Amount, type of resources needed to	- Interview	- Thematic analysis
implement		
Practicality		
Factors affecting implementation ease or	- Interview	- Thematic analysis
difficulty	- Survey T2	- Descriptive statistics 
Positive/negative effects on people with	- Interview	- Thematic analysis
epilepsy and their family members	- Survey T2	- Descriptive statistics 
Ability of parents/guardians to carry out	- Interview	- Thematic analysis
intervention activities	- Survey T2	- Descriptive statistics 
Expansion		
Fit with organizational goals and culture	- Group session	- Videotaped and thematic analysis
treatment of people with epilepsy		
Disruption due to expansion component	- Group session	- Videotaped and thematic analysis
	- Interview neurologist	- Thematic analysis
Limited-efficacy testing		
Health-related QoL	- EQ-5D-5L	- Check on normally distributed data
		- Descriptive statistics 
		- Paired samples T-test
Caregiver Strain Index (CSI)	- CSI	- Check on normally distributed data
		- Descriptive statistics 
		- Paired samples T-test
Pittsburgh Sleep quality index (PSQI)	- PSQI	- Descriptive statistics 

- Repeated measures ANOVA (if necessary multiple imputation)
- post-hoc test (Turkey's HSD)

- 1 = Median, mode, range, highest and lowest value
- 2 = Sensitivity, positive predictive value, false alarm rate (compared with results NightWatch analysis)
- 3 = Mean (with SD) or median (with IQR), mode, variance and range

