To evaluate SDD feasibility, we will compare parental strain, quality of sleep and QoL during the non-exposure period and exposure period [22]. Based on a survey after the exposure period, we will calculate retention rate.

After the exposure period, we will offer the parents/guardians and children ≥12 years of age two options, based on the diagnostic performance of the NightWatch in their child.

- 1. In case of bad performance, we will offer a second-2-month period of monitoring in case we noted that an individualized adjustment of the algorithm (i.e. threshold adjustments for heart rate & accelerometry settings) using the data from the exposure period results in a substantial improvement. We will prospectively test the diagnostic performance of the adjusted algorithm prospectively and compare results between both periods.
- 2. In case of good performance, we will offer the parents/guardians the possibility to keep the NightWatch for further use, under certain conditions. (See 11.4 Ethics)

[figure not shown]

Figure 1: Study design.

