# Focusing on:

- Intent to continue use (survey T0)
- Expectations (survey T0)
- Satisfaction (Survey T2 and semi-structured interview with parents/guardians and subjects)

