# Focusing on:

- Degree of execution, (Diary, semi-structured interview with parents/guardians and subjects and survey T2)
- Success or failure of execution (semi-structured interview with parents/guardians and subjects and survey T2)
- Amount, type of resources needed to implement (semi-structured interview with parents/guardians and subjects)

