# **Limited-efficacy testing**

The parameter *Limited-efficacy testing* is defined as:

The extent in which the NightWatch shows a promise of being successful on key intermediate variables (quality of life, stress, sleep, and strain) in people with epilepsy and their parents/guardians.

Focusing on Intended effects of the NightWatch on key intermediate:

- Health-related QoL in people with epilepsy and their parents/guardians, including EQ-5D-5L [27] (Survey T0 and T2)
- Strain and sleep, including Caregiver Strain Index (CSI) [28] and Pittsburgh Sleep Quality Index (PSQI) [29] (Survey T0 and T2).

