#### **Questionnaires & interviews**

During the study (T0 and T2), parent(s)/guardian(s) will be asked to complete several questionnaires about their experiences with NightWatch, quality of life, stress and quality of sleep. This will take 40 minutes for each time period (T0 and T2). The questionnaires will be presented in an online tool. Parent(s)/guardian(s) will give their consent to use their email address for access to this tool. A subgroup of parent(s)/guardian(s) will be invited to participate in a semi-structured interview focusing on feasibility of NightWatch and the impact of the SDD on family life. This interview will take one hour. Parent(s)/guardian(s) can indicate their availability to participate on the informed consent form. Based on all evaluations, researchers will decide which perspective will gain deeper understanding about the feasibility and impact of NightWatch. The researchers will select parents/guardians based on maximum variation.

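### Table 3 summarises its Survey T0 and T2 rows without counts or percentages, so a yes/no item would read the same at 52% and at 98%

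*Combined protocol and SAP*

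**What the plan says.** Feasibility of NightWatch is a secondary objective (protocol section 2). Section 10.2 sends its reporting to one table: "Feasibility and utility of the NightWatch will be presented, using descriptive statistics (see table 3".

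Table 3 has ten entries sourced to Survey T0 or Survey T2, and all ten carry footnote 1. They are satisfaction, intent to continue use, expectations, perceived demand (at T0 and again at T2), degree of execution, success or failure of execution, factors affecting ease or difficulty, positive/negative effects, and ability of parents to carry out the activities. Footnote 1 reads: "1 = Median, mode, range, highest and lowest value".

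Other feasibility data are handled differently. EQ-5D-5L, CSI and PSQI use footnote 3: "3 = Mean (with SD) or median (with IQR), mode, variance and range". The diary entries use footnote 2. The MCQ and PCQ are analysed under section 10.3.

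One proportion is planned outside Table 3, in section 3: "Based on a survey after the exposure period, we will calculate retention rate". It has no row in Table 3, and section 10 does not define it.

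Section 8.1.2 names the sources of two central items: "Success or failure of execution (semi-structured interview with parents/guardians and subjects and survey T2" and "Satisfaction (Survey T2 and semi-structured interview with parents/guardians and subjects". The response format of these survey items is not given anywhere.

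**The concern.** A reader of a home feasibility study will ask what share of families managed to use the device, were satisfied with it and see a need for it. Footnote 1 lists statistics of location and extremes only. The highest and lowest values largely repeat the range, and unlike footnote 3 there is no SD or IQR to show spread.

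The interviews cannot fill the gap. They cover a subgroup, and section 8.3 says how it is chosen: "The researchers will select parents/guardians based on maximum variation". That suits thematic analysis but does not estimate a share of all families. No other part of the plan commits to a share for success, satisfaction or perceived demand.

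If percentages are added only after the data are seen, the choice of items and cut-points is open to selection. Naming them now removes that.

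**Working it through.** **Inputs**
- Statistics: footnote 1 of Table 3.
- Enrolment: 60 children (sections 3 and 4.1).
- Drop-out for the feasibility part: about 30% (section 4.4), so 60 × (1 − 0.30) = 42 families.
- Response formats: not given. The cases below are assumptions.

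The plan states no target or precision for the survey items, so there is no figure to reproduce. Its one precision figure, 384, is 1.96² × 0.25 / 0.05² = 384 and concerns seizure detection.

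**Case 1: a yes/no item.** Code success 1 and failure 0, with k successes among N respondents.
- Median = 1 and mode = 1 whenever k > N/2.
- Lowest = 0 whenever k < N; highest = 1 whenever k ≥ 1; range = 1 − 0 = 1.

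So every k from N/2 + 1 to N − 1 gives the same output: median 1, mode 1, lowest 0, highest 1.

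| N | Smallest k | Largest k | Different results with the same output |
|---|---|---|---|
| 60 | 31 (51.7%) | 59 (98.3%) | 59 − 31 + 1 = 29 |
| 42 | 22 (52.4%) | 41 (97.6%) | 41 − 22 + 1 = 20 |

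The output changes only at the edges: at exactly half (median 0.5, two modes), below half (median and mode become 0) and at 100% (lowest becomes 1).

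**Case 2: an unordered item**, for example a list of factors that helped or hindered use. The categories have no order, so a median, range, highest or lowest value is undefined in substance. Only the mode carries information.

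**Case 3: a five-point graded item**, with 4 or 5 counted as favourable. These counts for scores 1 to 5 all give median 4, mode 4, range 1 to 5:

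| N | Counts | Favourable share |
|---|---|---|
| 60 | 1, 0, 28, 29, 2 | 31/60 = 51.7% |
| 60 | 1, 0, 0, 30, 29 | 59/60 = 98.3% |
| 42 | 1, 0, 19, 20, 2 | 22/42 = 52.4% |
| 42 | 1, 0, 0, 21, 20 | 41/42 = 97.6% |

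These distributions were chosen to match, so they show that the outputs can coincide, not that they will. The IQR would separate the two at N = 60. The 15th and 16th ordered answers are 3 in the first and 4 in the second; the 45th and 46th are 4 and 5. The IQR is therefore 3 to 4 against 4 to 5.

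**With n/N and a 95% Wilson interval**

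| Result | Share | 95% interval |
|---|---|---|
| 31/60 | 51.7% | 39.3 to 63.8 |
| 59/60 | 98.3% | 91.1 to 99.7 |
| 22/42 | 52.4% | 37.7 to 66.6 |
| 41/42 | 97.6% | 87.7 to 99.6 |

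A mid-range result would also be usable: 48/60 = 80% (68 to 88) and 34/42 = 81% (67 to 90).

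**The case against.** The strongest reply is that nobody outside the trial has seen the survey. The row names are areas of focus, not questions. The domains are defined by extent, and one item is a degree of execution, which points to graded answers. Median and range are an ordinary summary for those, and they do carry information about level. This stands: identical output is certain only for yes/no items, and that format is an assumption. The name of the success-or-failure item suggests it but does not prove it.

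The second reply is that nothing forbids percentages. Individual answers are collected, no threshold or test depends on them, and a frequency table can be made at any time. This also stands as far as it goes. A reader might infer that the trial will be unable to state these shares; the documents support only that the plan does not commit to stating them.

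Three further stronger readings are tempting and do not hold:
- **That every survey result is affected.** Section 8.1.2 also attaches a survey label to the scales, as in "Strain and sleep, including Caregiver Strain Index (CSI) [28] and Pittsburgh Sleep Quality Index (PSQI) [29] (Survey T0 and T2", but Table 3 gives these footnote 3. The MCQ and PCQ fall under section 10.3.
- **That these rows are the only quantitative feasibility data from all families.** The scale scores, the diary and the hours per night that NightWatch is on are quantitative too.
- **That the plan offers no proportion on continued use.** Section 3 plans a retention rate, and footnote 1 does not restrict it. The fair criticism is that its definition and denominator are missing.

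**Conclusion.** The point holds for the ten Table 3 entries sourced to Survey T0 or T2. Section 10.2 refers to Table 3, and footnote 1 lists statistics that leave out the share of families giving each answer. For a yes/no item the loss is nearly complete: 52% and 98% give the same output at 60 or at 42 respondents. For an unordered item most of the listed statistics have no meaning. For a graded item the ambiguity is possible rather than inevitable.

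This rests on two assumptions: the response formats, and 42 respondents after drop-out. The count of respondents matters little, since the range of hidden results is about the same at 60.

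Intent to continue use is surveyed at T0 only, before the device is installed. A percentage there would describe what families expected, not a wish to continue after use.

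The matter concerns descriptive secondary outcomes and leaves the primary performance endpoints untouched. It should be changed because the correction is small and the shares are what the feasibility objective needs.

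**What to change.** Replace footnote 1 with: *number and percentage (n/N) in each response category, with a 95% Wilson interval for the pre-named favourable category of the main items (success, satisfaction, perceived demand); median and IQR in addition for ordinal items.* Drop median and range for yes/no and unordered items. Name the favourable category of each main item before the data are analysed.

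Add a Table 3 row for the retention rate of section 3, with a definition and a denominator, reported as n/N with a 95% interval. Label the T0 result for intent to continue use as a pre-use answer.

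The cost is one footnote, one row and one label, and slightly longer results tables. No further data are collected.

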#### 10.3 Other study parameters

Economic evaluation NightWatch

This economic evaluation will involve a combination of a cost-effectiveness analysis (CEA) and a cost-utility analysis (CUA). Additional costs and additional outcomes will be compared before and after implementation of NightWatch in a family home.

In the CEA, effects are presented in clinical outcomes and the incremental cost-effectiveness ratio (ICER). The primary outcomes measure for the cost-utility analysis will be QALYs, based on the EuroQol utility scores.[33]

We will assess intervention costs, healthcare costs, patient and family costs, and costs outside the health care sector. We have developed an adjusted version of the Medical Consumption Questionnaire (MCQ) and the Productivity Costs Questionnaire (PCQ) especially designed for parents or representatives of children with epilepsy. The valuation of healthcare costs, patient and family costs will be based on the updated Dutch manual for cost analysis in healthcare research. This manual recommends using standardized cost prices.[34]

A baseline analysis will be performed to examine the comparability of groups at baseline for both costs and outcomes. If necessary, methods will be applied to control for differences in base. To investigate whether data are normally distributed a Kolmogorov-Smirnov test will be performed. Depending on the results either parametric (t-tests) or bootstraps will be used. The uncertainty of the Increment Cost Effectiveness Ratio (ICER) will be checked by non-parametric bootstrapping. The bootstrapped cost-effectiveness ratios will be subsequently plotted in a cost-effectiveness plane. The choice of treatment depends on the maximum amount of money that society is prepared to pay for a gain in effectiveness, which is called the ceiling ratio. Therefore, the bootstrapped ICERs will also be depicted in a cost-effectiveness acceptability curve showing the probability that NightWatch is cost-effective using a range of ceiling ratios. Additionally, to demonstrate the robustness of our base-case findings a multi-way sensitivity analyses will be performed.

# 10.4 Interim analysis (if applicable)

Not applicable.

#### 11 ETHICAL CONSIDERATIONS

#### 11.1 Regulation statement

The study will be conducted according to the principles of the Declaration of Helsinki (most recent version, date19-10-2013) and in accordance with the Medical Research Involving Human Subjects Act (WMO).

#### 11.2 Recruitment and consent

Subjects will be recruited in one of the epilepsy centers (SEIN, Kempenhaeghe, UMCU). The principal investigator will inform the neurologists from these centers about the study, before recruitment. After reviewing in- and exclusion criteria, the subject and/or parent(s) or guardian(s) will be informed about the study by their neurologist. All subjects and parent(s)/guardian(s) will receive an information letter with extensive information on the study, adjusted to age. Subjects and parent(s)/guardian(s) will be approached by researchers after a minimum of one week, to answer all questions and schedule an informed consent meeting (in person or by telephone) if they show interest. During this meeting, the researcher will explain everything about the study and parent(s)/guardian(s) can sign informed consent (with the researcher or at home, which will then be send to the researcher). Subjects between 12 and 16 years will give a co-consent in addition to the informed consent of their parents/guardians, if they are able to do so.

#### 11.3 Objection by minors or incapacitated subjects (if applicable)

We will make sure that a minor or incapacitated subject will never be forced to participate in our trial. Subjects aged 12-16 must give a co-consent in addition to the informed consent of their parent(s)/representative(s). The subject can only participate if both parties have given consent. Younger subjects (age 4-12) will be informed about the study in the best way we can (by means of a specific information letter, adjusted by age). If a minor or incapacitated subject gives any objection against participation, the subject will not be included in the study. Next to that, all subjects will be able to stop participating in the study, at any moment during the study. When the subject is able to communicate this (non)verbally, the wish of the subject will be honored. If the NightWatch is experienced as a nuisance, or makes the subject uncomfortable, the device will be removed in consultation with the parent(s)/representative(s).

# 11.4 Benefits and risks assessment, group relatedness

Implementing SDD is not considered to pose any substantial risks. Study participation can be a burden for the family (especially the parents/guardians) though, due to impact of the devices on privacy, impact of false alarms and time spent on the questionnaires &

interviews. Participation does, however, also offer better insight for the parents/guardians in the actual nocturnal seizure activity of their child, demonstrates the added value of the NightWatch and may help them to timely alert to a major seizure. When actual seizure activity is not consistent with the parent's expectations, this information can be confronting. All study results will be shared with the attending neurologists, so parents/guardians will be able to discuss this problem.

We will inform subjects and parent(s)/guardian(s) as good as possible on the impact of the study design on their privacy. It can be quite a burden to have a camera running in your (child's) room every night. To minimize this burden, we will give the subject and parent(s)/guardian(s) the opportunity to delete sensitive video or audio material from the storage data before it is send to the researchers. To prevent the risk of data getting lost, we do not allow subjects or parent(s)/guardian(s) to delete the material themselves. Every 1-2 weeks, when a trial nurse comes to their home to switch the external hard disk for an empty one, they are able to delete any footage they want, without any consequences. If subjects of parent(s)/guardian(s) do not want the trial nurse to see or hear the sensitive material, they can simply refer to a specific night, or time-window during a night, which will then be deleted by the trial nurse. If they wish to stop the recordings, they can contact the researcher to discuss which recordings should be stopped and those will be switched off immediately.

If a high frequency of false alarms causes a big burden on parent(s)/guardian(s), they can contact the researcher to discuss this problem. The researcher can then offer them the possibility to switch off the audible alarms. Because the annotation process takes some time, we are not able to give feedback on the reason for these false alarms, and if they are really false alarms, at that time. When the analyzation process is completed, the researchers will give the parent(s)/guardian(s) the opportunity to look at the recordings of their child to learn more about their seizures and reasons for false alarms.

At the end of the study, we will share the performance data of NightWatch with the subject's neurologist. He/she will invite the subject and/or his/her parent(s)/guardian(s) to discuss this performance and user experiences. As an objective third party, the neurologist can then advise them to keep NightWatch for further use or might advise to use another seizure detection device.

According to the performance of NightWatch, we will offer the following options at the end of the study:

In case of good performance, combined with satisfying use, NightWatch can give the family a benefit. In these cases, we would like to offer them the possibility to keep NightWatch for further use. We believe that offering NightWatch for free or a small amount of money can give an undesirable financial incentive to participate. It should be noted that currently none of the seizure detection devices are reimbursed. The most frequently sold seizure detection device (bed sensor) that was shown to have a poorer performance in our previous trial (LICSENSE NTR4115) has a higher cost price (€1700,-) compared to the NightWatch (€1500,-). For the above reasons, we found a 50% reduced rate of €750,- to be reasonable, since this is equal to the production costs. Besides, Livassured will offer a two year guarantee for the service and support of the device.

In case of bad performance, we will assess whether better performance can be obtained using a tailored algorithm. To this end we will review all trial data of the participant and evaluate the effects of altering the algorithm thresholds. If this is likely to result in a substantial improvement, we will offer participants a second 2-month intervention period with a tailored NightWatch algorithm. At the end of this trial we will once again share the results with the family and the treating neurologist. If the performance has improved we will offer the NightWatch at reduces rate of € 750,-.

